4.1 Complementary Information for Endpoint Assessment Method

Not applicable.

4.2 Complementary Information on Derived Endpoints: Calculation Methods

4.2.1 Safety

4.2.1.1 Solicited Reactions

4.2.1.1.1 Daily Intensity

All daily records for solicited reactions will be derived into daily intensity according to the following classification: None, Grade 1, Grade 2, Grade 3, or Missing (Unknown).

For the derivation of daily intensities, the following sequential steps will be applied:

- 1) Solicited reactions (except Fever/Pyrexia) with CRF presence recorded as "No" and with all daily records missing (Unknown) then all daily intensities will be derived as None.
- 2) For non-measurable solicited reactions, daily intensities will correspond to daily records reported in the clinical database. For measurable solicited reactions the daily measurements reported in the clinical database will be converted based upon the intensity scales defined in the protocol; this assumes a reaction that is too large to measure (non-measurable, "NM") is Grade 3.Note the intensity could be considered "None" (not a reaction) in the analysis despite being considered a reaction by the investigator (e.g., swelling measurement > 0 mm but < 25 mm in adults).

Note: The maximum intensity on the ongoing period is derived from the record of the maximum intensity/measurement after the end of the solicited period following the rule described above.

Confidential/Proprietary Information Page 30 of 40

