For solicited reactions, the denominator will be the total number of participants who have nonmissing data for the endpoint considered.

For unsolicited AEs, the denominator will be the total number of participants who were vaccinated.

In terms of contents, solicited reactions will be presented by time to onset, maximum severity, number of days of occurrence and action taken; unsolicited AEs will be presented by causal relationship, time of onset, maximum severity and duration; SAEs will be presented by causal relationship, seriousness and outcome.

Subgroup analyses will also be performed; in particular, the main safety endpoints will be described according to age subgroups (3 to 5 and 6 to 8 years), previous vaccination status, sex and race, as appropriate according to number of participants in the respective subgroups.

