4.2.1.1.2 Maximum Intensity

Maximum overall intensity is derived from the daily intensities computed as described in Section 4.2.1.1 and is calculated as the maximum of the daily intensities over the period considered.

4.2.1.1.3 **Presence**

Presence is derived from the maximum overall intensity over the time period considered:

- None: No presence
- Grade 1, Grade 2, or Grade 3: Presence
- Missing or Unknown: Missing presence

Participants with at least one non-missing presence for a specific endpoint will be included in the analysis. Conversely, those without a non-missing presence will not be included in the analysis of the endpoint.

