4.2.1.2 Unsolicited AEs

4.2.1.2.1 **Presence**

An observation will be considered an event if it has at least a verbatim term and is not a Grade 0 intensity event.

Grade 0 events are not included in safety analysis but are included in separate listings.

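### For solicited reactions other than fever, the SAP uses the CRF presence field when it says No but ignores it when it says the reaction occurred, so any 'present, no daily data' record lowers the reported percentage

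*SAP*

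**What the plan says.** SAP 4.2.1.1.1 derives daily intensity in sequential steps. Step 1 applies to "Solicited reactions (except Fever/Pyrexia) with CRF presence recorded as" No: such a record "and with all daily records missing (Unknown) then all daily intensities will be derived as None". Step 2 covers the rest and does not refer to the presence field: "For non-measurable solicited reactions, daily intensities will correspond to daily records reported in the clinical database", and measurements are converted by the protocol's grading scales.

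SAP 4.2.1.1.3 then works from intensity alone: "Presence is derived from the maximum overall intensity over the time period considered". Its last category is "Missing or Unknown: Missing presence", and it adds: "Conversely, those without a non-missing presence will not be included in the analysis of the endpoint". SAP 3.4.3 agrees: "For solicited reactions, the denominator will be the total number of participants who have nonmissing data for the endpoint considered".

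No other section supplies a rule. SAP 3.4.5.1.3 sends missing solicited intensity back to 4.2.1.1, and 3.4.5.1 says that safety data are in general not imputed. For unsolicited AEs, 4.2.1.2.1 says: "An observation will be considered an event if it has at least a verbatim term and is not a Grade 0 intensity event". A missing unsolicited grade is left missing under 3.4.5.1.3, so the event still counts.

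**The concern.** When all daily records are missing, the CRF presence field is the only information left on whether the reaction occurred. The SAP accepts that field in one direction only. An answered No keeps the child as a non-case. An answer that the reaction occurred is not used, and the child is removed.

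Solicited reactions are a secondary safety endpoint (listed as key secondary in the protocol synopsis). The same derivations feed the interim safety summaries for the firewall committee, because SAP 3.5.1 refers to 4.2.1. Safety is descriptive, so the percentages are themselves the result. A one-directional loss of cases goes straight into the reported reactogenicity.

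**Working it through.** The plan gives no figure for missing diary data, so there is none to reproduce. The check runs record types through the rule and then does the algebra.

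**1. The rule applied.**

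| Reaction | CRF presence | Daily records | Derived result |
|---|---|---|---|
| Not fever | No | all missing | None; kept as non-case |
| Not fever | Present | all missing | Missing; dropped |
| Not fever | Present | at least one graded day | case; kept |
| Fever | No | all missing | Missing; dropped |
| Fever | Present | all missing | Missing; dropped |

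The asymmetry is confined to reactions other than fever.

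**2. Inputs.** Let r be the true reaction rate. Protocol Table 2.1 gives, for ages 6 to 8 in an earlier trial, 43% for injection site pain and 18% for headache. Let m be the share of reactors recorded as present with no daily data. The documents do not give m; 2%, 5% and 10% are assumed.

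**3. Formula.** Reactors kept are r(1 − m), and non-reactors kept are 1 − r. The reported rate is r(1 − m) / [r(1 − m) + (1 − r)]. This is below r whenever m > 0 and 0 < r < 1, and equals r when m = 0.

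**4. Results.**

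| r | m = 2% | m = 5% | m = 10% |
|---|---|---|---|
| 43% | 0.4214/0.9914 = 42.5% | 0.4085/0.9785 = 41.7% | 0.3870/0.9570 = 40.4% |
| 18% | 0.1764/0.9964 = 17.7% | 0.1710/0.9910 = 17.3% | 0.1620/0.9820 = 16.5% |

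As a share of all children, these records are f = r × m. For r = 43%, that is 0.86% at m = 2% and 4.3% at m = 10%. In terms of f, the reported rate is (r − f)/(1 − f). At f = 1%, 43% becomes 0.42/0.99 = 42.4% and 18% becomes 0.17/0.99 = 17.2%, both less than 1 point lower.

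**5. Between arms.**
- Take true rates of 43% and 38% (illustrative) with m = 5% in both arms. The reported rates are 41.75% and 0.361/0.981 = 36.80%. The difference moves from 5.00 to 4.95 points.
- Take a true 43% in both arms with f = 2% in one and 1% in the other. The reported rates are 0.41/0.98 = 41.84% and 0.42/0.99 = 42.42%, a spurious difference of about 0.6 points.

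**6. Scale.** With 706 per arm, the 95% half-width at 43% is about 1.96 × √(0.43 × 0.57/706) = 3.7 points.

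**The case against.** The strongest reply is that the bias may be nil. It needs children recorded as present with every daily record unknown, and the plan reports none. Protocol 8.3.2 has the site interview the parent about incomplete or unclear entries and enter what the diary lacks. The CRF may not even accept such a record; its checks are not in the documents. This stands as a limit on size. It does not supply the missing rule.

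A second reply is that non-reactors with neither a CRF answer nor daily data are also dropped, which pushes the rate up. That does not cancel the effect. Reactors with no CRF answer are dropped in the same way. If a share k of both groups is lost like this, the factor (1 − k) multiplies every term of the formula and drops out. The imbalance comes only from using an answered field in one direction.

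A third reply is that keeping the No children is sound, because No is an observed answer. That is right; the fault lies in the missing counterpart.

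A reader might go further and infer that the SAP resolves missing safety data only toward 'no reaction'. The documents do not support that. The children at issue are left out and not recoded as non-cases. A reaction too large to measure is graded 3 (4.2.1.1.1). A missing causal relationship is taken as related (3.4.5.1.2), and an unsolicited AE with missing onset is counted within 28 days (4.2.1.2.4).

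A reader might also infer that a child recorded as present, with some days None and the rest missing, is counted as having no reaction. That holds only if the maximum ignores missing days. SAP 4.2.1.1.2 does not say so, which makes it a gap in the specification and not an established error.

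**Conclusion.** The point holds in conditional form. For solicited reactions other than fever, each 'present, no daily data' record lowers the occurrence percentage, and nothing else in the SAP repairs this. On the assumed range of 2% to 10% of reactors, the shortfall is 0.5 to 2.6 points at a true 43% and 0.3 to 1.5 points at a true 18%. With no such records it is zero. The range is an assumption, and the protocol's data collection steps suggest that the real number is small.

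A reader might take this to mean that reactogenicity is certainly understated, for every reaction, and that the vaccine comparison is distorted. The documents support none of these. The count is unknown and fever is exempt. The between-arm difference barely changes when rates and missingness are similar; a shift of about 0.6 points needs unequal missingness such as 2% against 1% of all children. Safety is descriptive (SAP 3.4.3), so no test, margin or power figure depends on the rule.

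The change is still worth making before database lock. It follows the SAP's own convention for ungraded unsolicited AEs. SAP 4.2.2.6 shows the present contrast: among AEs leading to discontinuation, a missing grade counts for an unsolicited event but not for a solicited one.

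**What to change.** In SAP 4.2.1.1.1 and 4.2.1.1.3, for solicited reactions other than fever:

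- Where CRF presence is recorded as present and all daily records are missing, set presence to Yes and intensity to Missing. Count the child in the numerator and denominator of the occurrence percentage.
- For these records, show time of onset, days of occurrence and ongoing status as missing, since 4.2.1.1.4 to 4.2.1.1.7 derive them from daily intensity.
- Where presence is recorded as present, some days are missing and no known day is Grade 1 or higher, state that the child is not derived as None, unless a recorded measurement falls below Grade 1.
- Report the number of such records by arm.

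Keep the limit to non-fever reactions. Step 1 does not keep fever records marked No, so adding only the present ones would create the opposite imbalance.

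The cost is a few sentences in the SAP, some programming for the derived variables, a missing category in the solicited tables, and slightly higher reported reaction rates. Sample size and the primary analysis are unaffected.

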4.2.1.1.2 Maximum Intensity

Maximum overall intensity is derived from the daily intensities computed as described in Section 4.2.1.1 and is calculated as the maximum of the daily intensities over the period considered.

4.2.1.1.3 **Presence**

Presence is derived from the maximum overall intensity over the time period considered:

- None: No presence
- Grade 1, Grade 2, or Grade 3: Presence
- Missing or Unknown: Missing presence

Participants with at least one non-missing presence for a specific endpoint will be included in the analysis. Conversely, those without a non-missing presence will not be included in the analysis of the endpoint.

4.2.1.1.4 Time of Onset

Time of onset is derived from the daily intensities computed as described in Section 4.2.1.1. It corresponds to the first day with intensity of Grade 1, Grade 2, or Grade 3.

Note: If a reaction is not continuous (i.e., reaction occurs over two separate periods of time intervened by at least one daily intensity Missing or None) then the time of onset is the first day of the first occurrence.

Time of onset period is displayed as, D01-D04, D05-D09.

4.2.1.1.5 Number of Days of Occurrence During the Solicited Period

Number of days of occurrence over the period considered is derived from the daily intensities computed as described in Section 4.2.1.1. It corresponds to the number of days with daily intensities of Grade 1, Grade 2, or Grade 3. Number of days of presence on the solicited period with a specified intensity may also be derived.

4.2.1.1.6 Overall Number of Days of Occurrence

If a reaction is ongoing at the end of the solicited period, then the overall number of days of presence is derived from the daily intensities and the end date of the reaction after the end of the solicited period. The overall number of days of presence is:

• (End date - vaccination date) + (number of days of presence within the solicited period) - length of the solicited period + 1

If the end date is missing or incomplete (contains missing data), the overall number of days of presence will be considered as Missing.

4.2.1.1.7 Ongoing

Confidential/Proprietary Information Page 31 of 40 Ongoing is derived from the last daily intensity of the solicited period computed as described in Section 4.2.1.1 and the maximum intensity on the ongoing period. The investigator's ongoing flag is not used because the measurement will determine the ongoing status of the reaction.

- Ongoing: if the last daily intensity of the solicited period is at least Grade 1 and the maximum intensity on the ongoing period is at least Grade 1
- Not ongoing: if the last daily intensity of the solicited period is None or the maximum intensity on the ongoing period is None.
- Missing: all other conditions (in this case, it is not included in the denominator of the ongoing analysis in the safety tables).

4.2.1.2 Unsolicited AEs

4.2.1.2.1 **Presence**

An observation will be considered an event if it has at least a verbatim term and is not a Grade 0 intensity event.

Grade 0 events are not included in safety analysis but are included in separate listings.

4.2.1.2.2 Intensity

Intensity will be derived according to the following classification: None, Grade 1, Grade 2, Grade 3, or Missing

If the unsolicited AE is measurable and its preferred term is part of the list of solicited reactions, then the measurement is derived based upon and following the same rule of the intensity scales defined in the protocol for that measurable injection site or systemic reaction. Note: the intensity could be considered as "None" (not a reaction) in the analysis despite being considered a reaction by the investigator (e.g., swelling measurement >0 mm but < 25 mm in adults).

Intensity for the other unsolicited AEs will correspond to the value reported in the CRF.

The maximum intensity corresponds to the highest intensity for a unique term.

4.2.1.2.3 Last Vaccination

Last vaccination before an unsolicited AE will be derived from the pre-visit numbers provided in the clinical database and will be calculated as follows:

- If an unsolicited AE has a non-missing pre-visit number, the pre-visit number will be used to determine the last vaccination before the unsolicited AE
- If the pre-visit number is missing and the start date is complete (ie, including day), then the start date will be used to determine the last vaccination before the unsolicited AE
- If an unsolicited AE has a missing pre-visit number and a partial start date (at least day missing), the unsolicited AE will be considered as post injection 1.

Confidential/Proprietary Information Page 32 of 40

4.2.1.2.4 Time of Onset

Time of onset is derived from the start date of the unsolicited AE and the date of vaccination:

Time of Onset = start date of the unsolicited AE - date of vaccination + 1 (if D01 is the first vaccination day).

The time of onset is considered as missing only if one or both dates are missing or partially missing.

The unsolicited AEs will be analyzed "Within 28 days" after each vaccination, which corresponds to AEs with a time of onset between D1 and D29 or missing. An AE with missing time of onset will be considered to have occurred just after the vaccination, so will be included in these tables.

Time of onset period is displayed as D01-D04, D05-D08, D09-D15, D16 or later, and Missing.

Note: Unsolicited AE that occurred before vaccination (negative time of onset) or with a time of onset higher than defined above will not be included in analysis but will be listed separately.

4.2.1.2.5 **Duration**

Duration is derived from the start and end dates of the unsolicited AE:

• Duration = End date of unsolicited AE - start date of unsolicited AE + 1.

The duration is considered as missing only if one or both of the start and end dates of the unsolicited AE is missing or partially missing.

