An unsolicited AE is an observed AE that does not fulfill the conditions of solicited reactions, ie, pre-listed in the CRF in terms of diagnosis and onset window post-vaccination. For example, varicella or a solicited term such as headache starting after the solicited observation period (eg, headache starting on Day 10 post-vaccination in the case where headache occurring between the day of vaccination and the next 7 days is pre-listed in the protocol and CRF as a solicited reaction).

An unsolicited AR is an unsolicited AE that is considered related to an IMP.

Unsolicited AEs includes both serious (SAEs) and non-serious unsolicited AEs.

All unsolicited AEs occurring at and around the IMP injection/administration site are to be considered by default as related to the IMP administered at that site and are therefore referred as unsolicited injection/administration site ARs.

All unsolicited AEs which are not at and around the IMP injection/administration site, are referred as systemic unsolicited AE. For each unsolicited systemic AE, the investigator assesses the relationship to the IMP. Systemic AEs assessed as related to IMP are referred as systemic ARs.

Adverse Event of Special Interest (AESI):

An adverse event of special interest (serious or non-serious) is one of scientific and medical concern specific to the Sponsor's study intervention or program, for which ongoing monitoring and rapid communication by the investigator to the Sponsor can be appropriate. Such an event might warrant further investigation in order to characterize and understand it. Depending on the nature of the event, rapid communication by the study Sponsor to other parties (eg, regulators) might also be warranted.

Medically Attended AE (MAAE)

An MAAE is a new onset or a worsening of a condition that prompts the participant or participant's parent/legally acceptable representative to seek unplanned medical advice at a physician's office or Emergency Department. Physician contact made over the phone or by e-mail will be considered a physician office visit for the purpose of MAAE collection. This includes medical advice seeking during the study visit or routine medical care. This definition excludes pediatric check-ups, follow-up visits of chronic conditions with an onset prior to entry in the study, and solicited reactions.

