3.4.5.1.4 Start Date and End Date

Missing or partially missing start dates or end dates for unsolicited AEs (including SAEs) will remain missing and not be imputed. If the start date is missing or partially missing, the time of onset will be considered missing. If either the start date or end date is missing or partially missing, the duration will be considered missing.

Missing or partially missing end dates for ongoing solicited AEs will remain missing and not be imputed.

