4.2.1.2.7 Serious Adverse Events

An event will be considered as a serious event if "Yes" is checked for "Serious" in the CRF.

SAEs will be analyzed within 28 days after each vaccination, from D29 to 180 days after each vaccination, and within 180 days after each vaccination.

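### Late SAEs and AESIs with a partial start date are tabulated within 28 days of vaccination even when the recorded month rules that window out

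*SAP*

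**What the plan says.** Four SAP rules and one protocol definition act together.

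- **Partial dates.** SAP 3.4.5.1.4: "Missing or partially missing start dates or end dates for unsolicited AEs (including SAEs) will remain missing and not be imputed". It continues: "If the start date is missing or partially missing, the time of onset will be considered missing". SAP 4.2.1.2.4 repeats this: "The time of onset is considered as missing only if one or both dates are missing or partially missing". Neither section makes use of a known month or year.
- **28-day window.** SAP 4.2.1.2.4 defines the window as one that "corresponds to AEs with a time of onset between D1 and D29 or missing", and adds: "An AE with missing time of onset will be considered to have occurred just after the vaccination, so will be included in these tables".
- **SAEs are unsolicited AEs.** Protocol 10.2.1: "Unsolicited AEs includes both serious (SAEs) and non-serious unsolicited AEs". Protocol 8.3.6 has AESIs captured as SAEs.
- **SAE and AESI windows.** SAP 4.2.1.2.7: "SAEs will be analyzed within 28 days after each vaccination, from D29 to 180 days after each vaccination", followed by a combined 180-day analysis. SAP 4.2.1.2.8 sets the same windows for AESIs. Neither section says what to do with a missing onset.
- **Dose attribution.** Under SAP 4.2.1.2.3 the pre-visit number decides the dose when it is present. If it is missing and the start date is partial, "the unsolicited AE will be considered as post injection 1".

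**The concern.** Placing a wholly unknown onset in the early risk window is a common conservative convention, and it suits non-serious events that are collected for only 28 days. SAEs and AESIs are followed to 6 months after the last dose and are analysed in separate early and late windows. For these, the rule can put an event in a window that its own recorded month excludes. That is a misclassification against data already in the database, not caution about an unknown.

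What is at stake is the reading of the early-versus-late SAE and AESI tables, where an excess soon after vaccination would be looked for, and in two-dose children the per-dose tables. The interim safety summaries use the same derivations and are meant to cover data up to D29 after the last vaccination (SAP 3.5.1). A late event with a partial date would enter them as an early one.

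**Working it through.** The plan states no figure on this point, so the check is to trace the rule. The formula is the SAP's own: time of onset = start date − vaccination date + 1. All calendar dates below are assumed.

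**One-dose child.** Dose on 15 Oct 2022 (D1); SAE start recorded as February 2023, day unknown.

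- From 15 Oct to 1 Feb is 16 + 30 + 31 + 31 + 1 = 109 days, so the earliest possible onset is D110.
- Under the SAP, onset is missing, so the event is counted within 28 days. Its recorded month allows no day before D110.

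**Two-dose child.** Dose 1 on 10 Oct 2022, dose 2 on 7 Nov 2022, day of onset unknown, pre-visit number also missing. The SAP counts every row below within 28 days of dose 1.

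| Recorded month | Possible days after dose 1 | Possible days after dose 2 | What the month alone settles |
|---|---|---|---|
| Nov 2022 | D23 to D52 | −5 to D24 | Neither dose nor window |
| Dec 2022 | D53 to D83 | D25 to D55 | After dose 2; window ambiguous |
| Feb 2023 | D115 to D142 | D87 to D114 | After dose 2; later window |

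**How often the month would settle it.** This count assumes vaccination dates spread evenly from 1 September to 31 January, true onset spread evenly, and only the day missing; none of this is in the documents. Each vaccination date was paired with each true onset day, and the first of the onset month was taken as the earliest possible start.

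- True onset on D30 to D181: the month alone proves onset after D29 in about 90.5% of pairs.
- True onset on D2 to D181 after dose 2: the month alone proves onset after dose 2 in about 92% of pairs.

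These figures show how often the information needed would be available for a month-only date. They do not say how often such dates occur.

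**Weight of one event.** With 706 per arm planned (Protocol, Table 6.2), 1/706 = 0.14 percentage points. With about 183 per arm at the interim (SAP Table 3.2), 1/183 = 0.55 points.

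**The case against.** The strongest reply has four parts.

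1. **Partial SAE dates should be uncommon.** SAEs must reach the sponsor within 24 hours (Protocol 8.3.1). Parents receive a Memory Aid at the last active-phase visit, and it is reviewed at the 6-month call (Protocol 1.3, Tables 1.1 and 1.2). The investigator reviews the medical records of each event (Protocol 10.2.3). This stands. A reader might infer that late SAEs rest on a single interview and parental recall; the documents do not support that.
2. **The 28-day text may have been written for the general unsolicited-AE tables.** A note in SAP 4.2.1.2.4 leaves events with later onset out of the analysis, which cannot be meant for SAEs. This stands in part. That a missing-onset SAE is absent from the D29-to-180-day table is an inference. But SAP 3.4.5.1.4 names SAEs expressly, and no text sends a missing onset to the later window, so the inference is the natural reading.
3. **The dose error needs three conditions together:** a two-dose child (about half of participants), a partial date and a missing pre-visit number. This stands. A reader might infer that any partial date puts a post-dose-2 event under dose 1; SAP 4.2.1.2.3 prevents that whenever the pre-visit number is present.
4. **The consequences are contained.** The firewall committee receives a listing of all SAEs, including data beyond D29 (SAP 3.5.1 and 3.5.2.4), and weighs the totality of the information; the plan states no SAE-rate threshold. Missing onset is displayed as its own category, the rule is the same in both arms, and it can only add events to the early window. All of this stands. It limits the harm but does not correct a wrong count in a table.

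**Conclusion.** The point holds as a minor flaw in a derivation rule. As written, a late SAE or AESI with only the day missing is tabulated within 28 days against its own recorded month and, by implication, not in the later window. With a missing pre-visit number in a two-dose child, it also goes to dose 1.

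The number of events affected cannot be computed, because the documents do not say how often partial dates or missing pre-visit numbers occur; it is probably small. The window rule leaves within-180-day totals and SAE listings intact. Safety is descriptive (SAP 3.4.3), so no hypothesis test changes. What remains is that SAEs are likely to be few, so one misplaced event is visible: 0.14 points per arm at the end, 0.55 at the interim.

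Two larger readings are not supported. For a one-dose child, 152 of 181 follow-up days (84%) lie outside D1 to D29; a reader might take that as the share of events misplaced, but it is a share of follow-up time. Nor can a relative increase in the early SAE rate be stated, since it would rest on an invented number of true early events.

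**What to change.** Amend SAP 3.4.5.1.4, 4.2.1.2.3 and 4.2.1.2.4, with a cross-reference in 4.2.1.2.7 and 4.2.1.2.8. For SAEs and AESIs:

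- When the start date is partial, derive the earliest and latest possible onset from the known month and year, and from the pre-visit number where present.
- Dose: let the pre-visit number decide when present, as now. If it is missing, assign the event to dose 2 only when the whole possible interval lies after dose 2; otherwise keep dose 1.
- Window: use the later window only when the whole possible interval lies after D29 of the assigned dose; otherwise keep the 28-day default.

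In the two-dose example, February 2023 moves to the later window of dose 2, December 2022 moves to dose 2 but stays in its 28-day window, and November 2022 is unchanged.

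The cost is a few lines of SAP text and derivation code before database lock. No new data are needed, and ambiguous dates stay conservative.
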